9. STATISTICAL METHODOLOGY

9.1 General

Data listings will be provided for all data that is databased. Summary statistics and statistical analysis will only be presented for data where detailed in this SAP. For continuous data, summary statistics will include the arithmetic mean, arithmetic standard deviation, median, min, max and N; for log-normal data (e.g. the PK parameters: AUCs and C_{max}) the geometric mean and geometric coefficient of variation will also be presented. For categorical data, frequency count and percentages will be presented. Data listings will be provided for all participants up to the point of withdrawal, with any participants excluded from the relevant population highlighted. Summary statistics and statistical analyses will generally only be performed for participants included in the relevant analysis population. For the calculation of summary statistics and statistical analysis, unrounded data will be used.

Mean change from baseline is the mean of all individual participants' change from baseline values. Each individual change from baseline will be calculated by subtracting the individual participant's baseline value from the value at the timepoint. The individual participant's change from baseline values will be used to calculate the mean change from baseline using a SAS procedure such as Proc Univariate.

Data analysis will be performed using SAS® Version 9.4 or greater.

9.2 Demographics and Participant Disposition

Participant disposition will be listed. The demographic variables age, sex, race, ethnicity, BW, height, HbA1c and body mass index will be summarized and listed.

9.3 Pharmacokinetic Assessment

9.3.1 Pharmacokinetic Analysis

The PK parameter estimates will be performed by Lilly for LY3493269 and SNAC will be calculated using standard noncompartmental methods of analysis. The software and version used for the final analyses will be specified in the clinical study report.

The primary parameters for analysis will be C_{max} , AUC and t_{max} . The PK parameters for C_{max} and AUC(0-24) will be computed after the first, second, and third doses, with AUC(0- t_{last}) and AUC(0- ∞) also calculated after the third dose. Other parameters, such as half-life, apparent clearance, and apparent volume of distribution, may be reported.

The PK data will be provided by Eli Lilly and Company for the analysis.

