1.3. Schedule of Activities (SoA)

ii 90			Treatment Period									llow-	-up		
Study Activities	Screening		CR	RU Inpatie	nt Stay			Ou	tpatio	ent	Outpatient			Comments/	
Days	-28 to -2	-1	1	2	3	4	5	6	8	15 ± 1	29 ± 3	43 ± 3	ЕТ	Notes	
Study informed consent	X														
Medical history	X														
Physical examination	X														
Medical assessment			Р	P	P		X	X	X	X	X	X	X	Medical review and targeted examination, as appropriate.	
Height and weight	X		P		X				X	X	X	X	X	Height at screening only.	
Admit to CRU		X													
Discharge from CRU							X							At the investigator's discretion, participants may remain inpatient after Day 5.	
Outpatient visit to CRU								X	X	X	X	X	X		
Administer study drug			X	X	X									Refer to Section 6.1.1 for details	
Product palatability assessment			X	X	X									Refer to Section 8.11 for details	
AEs/concomitant medications	X	X	X	X	X	X	X	X	X	X	X	X	X		
Vital signs: supine BP/PR (h)	X		-0.5, -0.25, P, 1, 4, 6, 12	P, 1, 4, 12	-0.5, -0.25, P, 1, 4, 6, 12	X	X	X	X	X	X	X	X		
Body temperature	X		P	P	P										
ECG – single	X										X	X	X		
ECG – triplicate (h)			-0.5, -0.25, P, 1, 4, 6, 12	P, 1, 4, 12	-0.5, -0.25, P, 1, 4, 6, 12	X	X	X	X	X					
Clinical laboratory tests (fasted)	X		P				X		X	X	X	X	X	See Appendix 2 (Section 10.2) for details.	
HbA1c			P												

		Treatment Period									llow-	-up		
Study Activities	Screening		CR	U Inpatie	nt Stay			Ou	tpatio	ent	Outpatient			Comments/
Days	-28 to -2	-1	1	2	3	4	5	6	8	15 ± 1	29 ± 3	43 ± 3	ET	Notes
Point-of-care safety glucose samples (glucose analyzer)			Days 1 – 4: Pre-meals (breakfast, lunch, and dinner) and before bedtime			X	X						Days 5-6: Fasted samples collected before breakfast.	
LY3493269 PK sampling (h)			P, 0.5, 1, 1.5, 2, 2.5, 3, 4, 5, 6, 8, 12		P, 0.5, 1, 1.5, 2, 2.5, 3, 4, 5, 6, 8, 12	X	X	X	X	X	X	X	X	Days 15, 29, 43, and ET: Samples collected anytime during visit.
SNAC PK sampling (h)			P, 0.5, 1, 1.5, 2, 2.5, 3, 4, 5, 6, 8, 12		P, 0.5, 1, 1.5, 2, 2.5, 3, 4, 5, 6, 8, 12	X	X							
PD biomarkers (fasted) • Glucose, Insulin, and C-peptide			P		P		X		X	X	X			
Triglycerides – (fasted)			P		P		X		X	X	X			
Appetite VAS – (fasted)			P	P	P		X		X	X	X			
Immunogenicity			P							X	X	X	X	Day 1: Samples are collected within 30 min of the predose PK samples.
Pharmacogenetic sample			X											Obtained at any time on Day 1.
Nonpharmacogenetic stored samples – (fasted)			P		P		X		X	X	X			

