4.2. Scientific Rationale for Study Design

A population of healthy participants is selected to assess the safety and tolerability of LY3493269 for initiation of oral administration in humans prior to further investigations in participants with T2DM. Using a healthy participant population mitigates possible confounding effects of comorbidities and concomitant medications. Therefore, Study GZHF provides an unbiased assessment of safety, tolerability, and PK of LY3493269 administered as oral doses.

The study is intended to estimate a maximum tolerated exposure or establish that exposures exceeding the expected therapeutic range are tolerated via the oral route of administration. Additionally, the study will inform the target exposure range for subsequent oral dosing of LY3493269. Safety, tolerability, PK, and preliminary PD data will assist in identifying an appropriate dose range for subsequent clinical studies regardless of administration route.

A study design of once-daily oral dosing for 3 days will be employed to characterize oral PK behavior of LY3493269. The dosing duration of 3-days was selected after taking into consideration the following factors:

- low oral bioavailability expected from oral peptide formulations,
- the exceptionally high inter- and intra-individual variabilities in oral bioavailability expected of oral peptide formulations,
- the sensitivity of the bioanalytical assay, and
- once absorbed via the oral route of administration, LY3493269 systemic PK disposition should be similar regardless of route of administration, hence safety, tolerability, and PK data from the SC SAD study (GZHA) should be applicable to this study.

To predict the oral PK profiles for each cohort, extensive PK simulations were conducted. The PK profile following a single oral dose was deemed to be at risk of being highly variable and potentially returning lower than quantifiable concentrations at multiple time points. The simulation results did suggest that 3 days was adequate for a majority of PK profiles from participants in each cohort to remain above the quantification limit of CCI to yield meaningful PK results. The PK data from Study GZHA estimated the LY3493269 CCI . Therefore, PK exposures from a short dosing duration of 3 days from this study are not expected to reach steady state for the respective doses.

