8.5. Pharmacokinetics

Plasma samples will be collected for measurement of plasma concentrations of study intervention as specified in the SoA (Section 1.3).

A maximum of 2 samples may be collected at additional time points during the study if warranted and agreed upon between the investigator and the sponsor. The timing of sampling may be altered during the course of the study based on newly available data (e.g., to obtain data closer to the time of peak plasma concentrations) to ensure appropriate monitoring.

Instructions for the collection and handling of biological samples will be provided by the sponsor. The actual date and time (24-hour clock time) of each sample will be recorded.

Samples will be used to evaluate the PK of study intervention. Samples collected for analyses of study intervention plasma concentration may also be used to evaluate safety or efficacy aspects related to concerns arising during or after the study.

Genetic analyses will not be performed on these plasma samples. Participant confidentiality will be maintained.

Drug concentration information that would unblind the study will not be reported to CRUs or blinded personnel until the study has been unblinded.

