9.4.1. General Considerations

Data listings will be provided for all data that are databased. Summary statistics and statistical analysis will only be presented for data where detailed in the SAP. For continuous data (e.g., the demography data, clinical laboratory data, vital signs data, ECG data, appetite analysis data, and PD data), summary statistics will include the arithmetic mean, arithmetic standard deviation, median, minimum, maximum, and the number of observations; for log-normal data (e.g., the PK parameters: AUC during 1 dosing interval [AUC $\{0-\tau\}$] and C_{max}), the geometric mean and geometric coefficient of variation (%) will also be presented. For categorical data (e.g., the AE data and hypoglycemic classification data), frequency count and percentages will be presented. Data listings will be provided for all participants up to the point of withdrawal, with any participants excluded from the relevant population highlighted. Summary statistics and statistical analyses will generally be performed only for participants included in the relevant analysis population. For the calculation of summary statistics and statistical analysis, unrounded data will be used.

Mean change from baseline is the mean of all individual participants' change from baseline values. Each individual change from baseline will be calculated by subtracting the individual

participant's baseline value from the value at the time point. Baseline is defined to be Day 1 pre-dose measurements unless otherwise stated.

Data analysis will be performed using SAS® Version 9.4 or greater.

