9.4.4. Pharmacokinetic Analyses

Pharmacokinetic parameter estimates for LY3493269 and SNAC will be calculated using standard noncompartmental methods of analysis. The primary parameters for analysis will be C_{max} , AUC, and t_{max} . Pharmacokinetic parameters for C_{max} and AUC will be computed after the first, second, and third doses. Other parameters, such as half-life, apparent clearance, and

apparent volume of distribution, may be reported. If deemed necessary, additional model-based analysis may be performed for LY3493269 or data may be combined with Study GZHA for further analysis.

Pharmacokinetic dose proportionality for Days 1 and 3 will be explored separately. Log-transformed C_{max} and AUC of LY3493269 from Cohorts 1 to 3 will be evaluated separately for Days 1 and 3 using a power model (where log-dose acts as an explanatory variable) to estimate ratios of dose-normalized geometric means and corresponding 90% CIs. The estimated ratio of dose-normalized geometric means of PK parameters between the highest and lowest doses will be used to assess dose proportionality. A subinterval within the highest and lowest doses may also be considered for assessment of dose proportionality using the same approach. Additional details will be provided in the SAP.

The parameter t_{max} of LY3493269 and SNAC will be analyzed using a nonparametric method. All PK parameters will be summarized using descriptive statistics.

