10.2.1. Blood Sampling Summary

This table summarizes the approximate number of venipunctures and blood volumes for all blood sampling (screening, safety laboratories, and bioanalytical assays) during the study.

Protocol J1X-MC-GZHF Blood Sampling Summary

Purpose	Blood Volume per Sample (mL)	Approximate Number of Blood Samples	Approximate Total Volume (mL)
Screening tests ^a (local laboratory)	20	1	20
Clinical laboratory tests ^a (local laboratory)			
Study visit: Day 1	13	1	13
• Study visits: Days 5, 8, and 15	10	3	30
Follow-up visit	10	2	20
LY3493269 and SNAC pharmacokinetics (1 blood sample for both analytes)	3	38	114
Potential additional LY3493269 and SNAC pharmacokinetic samples	3	2	6
Blood discard for cannula patency	0.3	49	14.7
Point-of-care safety glucose (on-site)	0.3	18	5.4
Pharmacodynamics (central laboratory)			
• Glucose	2	6	12
• Insulin	2	6	12
• C-peptide	2	6	12
Mechanistic biomarker (central laboratory)			
Triglycerides	3.5	6	21
Pharmacogenetic sample (stored)	10	1	10
Nonpharmacogenetic sample (stored)			
• Plasma	2	6	12
• Serum	2.5	6	15
• P800	2	6	12
Immunogenicity	10	4	40
Total			369.1
Total for clinical purposes (rounded up to the	370		

Abbreviations: SNAC = salcaprozate sodium.

^a Additional samples may be drawn if needed for safety purposes.

10.3. Appendix 3: Adverse Events: Definitions and Procedures for Recording, Evaluating, Follow-up, and Reporting

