9.3.2 Pharmacokinetic Statistical Methodology

For all cohorts, log-transformed C_{max} , AUC(0-24), AUC(0- t_{last}) (Day 3 only), and AUC(0- ∞) (Day 3 only) parameters of LY3493269 on Days 1 (first dose) and 3 (third dose) independently will be evaluated using a power model (where log-dose acts as an explanatory variable, and SNAC fitted as a dichotomous variable in which the variable equals 0 for those doses with 300 mg SNAC, and 1 for those with 600 mg SNAC) to estimate ratios of dose-normalized geometric means and corresponding 90% confidence intervals (CIs). The estimated ratio of dose-normalized geometric means of PK parameters between the highest and lowest doses will be used to assess dose proportionality. The 90% CI will also be reported for the parameter of the SNAC variable. A subinterval within the highest and lowest doses may also be considered for assessment of dose proportionality using the same approach.

Example of the SAS code (for C_{max} and $AUC[0-24]$) for the analysis:

```
proc mixed data=xxx;
  class usubjid SNAC;
  model log_pk = log_dose SNAC / alpha=0.1 cl solution outpred=resids ddfm=kr;
  estimate 'xx mg' intercept 1 log_dose yy / alpha=0.1 cl; /*Log value of xx*/
  estimate 'zz mg - xx mg' log_dose pp / alpha=0.1 cl; /*Difference in log
values of zz and xx*/
  ods output solutionf=est;
  ods output estimates=estims;
run;
```

The LY3493269 parameter t_{max} will be analyzed non-parametrically using the Kruskal-Wallis test to investigate its independence, and, hence, dose proportionality, with the respective p-value reported. For each dose, 90% CIs for the median will also be reported.

Example SAS code is as follows:

```
proc nparlway data=xxx
  class dose;
  var pk;
  ods output KruskalWallisTest=krusk;
run;
```

For Cohorts 1 and 2, and 3 and 4 independently, log-transformed dose normalized C_{max} , $AUC(0-24)$, $AUC(0-t_{last})$ (Day 3 only), and $AUC(0-\infty)$ (Day 3 only) parameters of LY3493269 on Days 1 (first dose) and 3 (third dose) will be analyzed independently an analysis of variance model to assess dose proportionality. The model will include treatment as a fixed effect. The difference in least-square (LS) treatment means and respective LS means will be back transformed to produce the ratio of geometric means, and the 90% CIs of the LS means and difference between the means will be reported.

Example of the SAS code for the dose normalized analysis:

```
proc mixed data=xxx;
  class usubjid;

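### No PK sample is scheduled on Day 2, so dose-2 Cmax and AUC(0-24) cannot be computed and Day 1 AUC(0-24) has no data from 12 to 24 h

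*SAP*

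**What the plan says.** **Parameters promised.** SAP 9.3.1 specifies noncompartmental analysis and says that Cmax "and AUC(0-24) will be computed after the first, second, and third doses". Protocol 9.4.4 says that Cmax and AUC "will be computed after the first, second, and third doses". Protocol 9.4.1 names the parameter as "AUC during 1 dosing interval", which is 24 h under once-daily dosing.

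**Use in the models.** SAP 9.3.2 lists log-transformed Cmax and AUC(0-24) among the "parameters of LY3493269 on Days 1 (first dose) and 3 (third dose) independently will be evaluated using a power model". The dose-normalized analysis of variance in the same section uses the same parameters on the same two days. SAP Appendix 1 records that version 2.0 added Day 1 to the dose-proportionality analysis.

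**Sampling.** Protocol 8.5 makes the SoA (Section 1.3) govern PK sampling. The LY3493269 row has predose to 12 h on Day 1, an empty Day 2 cell, predose to 12 h on Day 3, and one sample each on Days 4, 5, 6, 8, 15, 29, 43 and at early termination (ET). The SNAC row has the same Day 2 gap and stops at Day 5. Vital signs and triplicate ECGs do have Day 2 times in that table.

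**Flexibility.** Protocol 8.5 adds: "A maximum of 2 samples may be collected at additional time points during the study", if warranted and agreed. Sections 4.1.2 and 6.6 also allow the sampling schedule to change.

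**The concern.** The plan commits to outputs that its own sampling schedule cannot supply. There are two consequences, of different weight.

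- **Dose 2.** Cmax and AUC(0-24) would be left empty for both analytes. These values enter no inferential model.
- **Dose 1.** This matters more. AUC is a secondary endpoint, and Day 1 AUC(0-24) is a modelled response. Its second half rests on no observation, while the Day 3 value can use the Day 4 sample, so the two days would be built on different data.

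Neither document says whether a Day 1 profile ending at 12 h is to be extrapolated, truncated or excluded. The only rule for values below quantification is in SAP 9.6.6, and it applies to the concentration-ECG analysis. Uneven handling between participants is a real risk: Protocol 4.2 describes single-dose profiles as at risk of being highly variable and "potentially returning lower than quantifiable concentrations at multiple time points".

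**Working it through.** **1. Sample count**

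Inputs: the LY3493269 PK row of the SoA; 38 samples at 3 mL from Protocol 10.2.1.

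- The table's own arithmetic reproduces: 38 × 3 = 114 mL, and the listed volumes sum to the stated 369.1 mL.
- Count from the SoA: 12 (Day 1) + 0 (Day 2) + 12 (Day 3) + 7 (Days 4, 5, 6, 8, 15, 29, 43) = 31, or 32 with ET.
- Difference: 38 − 31 = 7 draws, or 7 × 3 = 21 mL (6 draws with ET).
- Other rows of the blood table do match the SoA: glucose 4 × 4 + 2 = 18, PD 6, immunogenicity 4. The PK row does not.
- Adding a Day 2 predose sample gives 31 + 1 = 32. Adding a full 12-point Day 2 profile gives 31 + 12 = 43. Neither is 38.

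**2. What each dosing interval contains** (hours from dose 1)

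| Dose | Interval | Scheduled samples |
|---|---|---|
| 1 | 0–24 | predose to 12 h; none from 12 to 24 h |
| 2 | 24–48 | one, at 48 h (Day 3 predose) |
| 3 | 48–72 | predose to 12 h postdose, then Day 4 |

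After the 12-h sample the next is at 48 h, a gap of 48 − 12 = 36 h. That sample follows dose 2, so it cannot anchor the first interval. One trough gives no observed Cmax and no AUC for dose 2.

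**3. Size of the 12–24 h piece**

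The half-life is redacted; Protocol 2.2.1 shows only that it is in days. Assumed: half-life 48 to 168 h, first-order absorption with ka 0.5 to 2 per hour, one compartment, k = ln 2 / half-life:

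C(t) = ka/(ka − k) × [exp(−kt) − exp(−ka·t)]

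AUC(0–T) = ka/(ka − k) × [(1 − exp(−kT))/k − (1 − exp(−ka·T))/ka]

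Share from 12 to 24 h = 1 − AUC(0–12)/AUC(0–24):

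| Half-life | ka 0.5 | ka 1 | ka 2 |
|---|---|---|---|
| 48 h | 0.506 | 0.480 | 0.468 |
| 72 h | 0.519 | 0.494 | 0.482 |
| 120 h | 0.530 | 0.505 | 0.494 |
| 168 h | 0.534 | 0.510 | 0.499 |

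The ratio AUC(0–24)/AUC(0–12) is 1/(1 − share), from 1/(1 − 0.468) = 1.88 to 1/(1 − 0.534) = 2.15. Wider assumptions (half-life 24 to 168 h, ka 0.3 to 2) give shares of 0.43 to 0.57.

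**4. How much the handling rule matters**

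- Same day-scale extrapolation for everyone, without assay noise: imposing 168 h when the truth is 48 h gives +2.9 to +3.0%; imposing 48 h when the truth is 168 h gives −2.9 to −3.3%; holding the 12-h concentration flat gives +1.2 to +4.4%.
- Same truncation for everyone: the factor is nearly common to all doses and cancels in the dose-proportionality ratio, but a value reported as AUC(0-24) would be about half the true one.
- Mixed handling: if m of 8 participants in a cohort are truncated and the rest extrapolated, that cohort's geometric mean falls by a factor R^(m/8), with R the ratio above. For m = 2 this is 1.88^0.25 = 1.17 to 2.15^0.25 = 1.21. For m = 4 it is 1.88^0.5 = 1.37 to 2.15^0.5 = 1.47. These values of m are illustrative.

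**The case against.** **The blank cell may not be intended.** Two sections promise dose-2 parameters and the blood table holds seven more samples than the SoA, so a Day 2 series may have been omitted from the SoA. The cause is indeed open, and reconciliation should not presume that the SoA is right. But both PK rows are blank on Day 2, the later entries line up with their day columns, and the models use only Days 1 and 3. The mismatch holds whichever part is wrong.

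**No one plans to report AUC(0-12) as AUC(0-24).** True. The half-value figure is conditional on truncation, and a uniform extrapolation rule would cost only a few percent. The difficulty is that no rule is stated, and a terminal slope fitted to data ending at 12 h is weak for a half-life of days.

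**A 24-h sample would not rescue a profile already below quantification at 12 h.** This stands: a written rule is needed even if the sample is added.

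**The Day 4 sample carries no clock time.** Also fair. Treating it as 24 h after dose 3 is an inference, and the statement that Day 3 AUC(0-24) is sound depends on it.

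**The protocol already allows schedule changes and two extra samples.** That permission is discretionary. One draw could close the Day 1 interval, but two cannot supply a dose-2 profile.

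**The consequences are limited.** PK is secondary, the study is unpowered, and the sample count errs towards overstating blood volume. This limits the severity but does not remove the contradiction.

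**Conclusion.** The concern holds. As written, dose-2 Cmax and AUC(0-24) cannot be derived for LY3493269 or SNAC, and Day 1 AUC(0-24) enters the power model and the analysis of variance with no data from 12 to 24 h. Under the assumed half-life and absorption rates, about half of that parameter is unobserved. The main exposure is the missing rule and the resulting chance of uneven handling, rather than the choice among reasonable extrapolations.

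The 38 against 31 sample discrepancy follows directly from the documents and needs no assumption. Day 1 Cmax is unaffected, as are the Day 3 parameters if the Day 4 sample is taken about 24 h after dose 3. The primary endpoint is not touched. This should be fixed, but it does not undermine the study.

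**What to change.** 1. Add a Day 2 predose PK sample to the SoA, about 24 h after dose 1. Participants are inpatient, the draw is 3 mL, and it fits within the two extra samples in Protocol 8.5 and the sampling changes allowed in Section 6.6.
2. If it is not added, or for participants already dosed, use AUC(0-12) as the Day 1 response in both SAP 9.3.2 models and report Day 3 AUC(0-12) alongside it for comparison.
3. In either case, state in SAP 9.3.1 one rule, applied to every profile, for a last quantifiable concentration that falls before the end of the interval. Give the nominal time of the Day 4 sample.
4. Reconcile the SoA, Protocol 9.4.4, Protocol 10.2.1 and SAP 9.3.1. Remove dose-2 Cmax and AUC unless a Day 2 profile was intended; if it was, add it to the SoA. Make the PK sample count agree with the resulting schedule.

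Cost: one 3-mL inpatient draw per participant with a change to the SoA, or SAP wording only for the AUC(0-12) option, plus the text corrections to both documents.

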A dose-dependent increase in HR, which is consistent with the incretin class (Lorenz et al. 2017), was noted. While no clinically significant changes were noted in ECG results, 3 participants in Cohort 3 (1.5 mg) presented mild AEs of tachycardia. No significant changes in the BP measurements were noted. The maximum HR (supine) for all 3 participants occurred at 4 hours postdose; the HR for these 3 participants returned to below 100 bpm, ranging between 6 hours for one participant and Day 3 postdose for another.

Six participants received the 0.5-mg intravenous dose as planned. Mild events of decreased appetite and GI events such as abdominal distension and nausea were noted.

Preliminary PK data from the SC route indicated the median time of t_{max} was hours, close to proportional increase in exposures with increasing dose and a half-life of days, which is suitable for a weekly dosing interval.

Preliminary PD data suggest LY3493269 when administered SC may potentially reduce total body weight, appetite, and glucose concentrations during an oral glucose tolerance test.

Study J1X-MC-GZHB

Study J1X-MC-GZHB (GZHB) is a Phase 1, randomized, placebo-controlled, dose-escalation study investigating the safety, tolerability, PK, and PD of an LY3493269 formulation administered as 3 consecutive once-daily oral doses in healthy participants. In this study, the LY3493269 oral formulation contained sodium caprate (C10) as a permeation enhancer.

Four cohorts, each with 8 participants receiving LY3493269 and 2 receiving placebo, received the following study treatments:

- Cohort 1 participants received 8 mg LY3493269 or placebo plus 500 mg C10, as 2 capsules
- Cohort 2 participants received 24 mg LY3493269 or placebo plus 500 mg C10, as 2 capsules
- Cohort 3 participants received 48 mg LY3493269 or placebo plus 500 mg C10, as 2 capsules
- Cohort 4 participants received 24 mg LY3493269 or placebo plus 250 mg C10, as a single capsule

The last patient visit for this study was achieved on 28 December 2020, and data lock is anticipated in March 2021.

Preliminary safety data

No SAEs were reported in the study. Forty male participants received study treatments, of which 1 participant discontinued from the study due to nausea of moderate severity and which was considered related to study treatment. The safety profile for Study GZHB is similar to Study GZHA with the most frequent AEs being gastrointestinal AEs:

- Decreased appetite
- Nausea
- Abdominal distension

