4.1.2. Treatment Period

Study participants will be admitted to the CRU on Day -1 and adhere to an overnight fast.

Participants will be randomly assigned to treatment, followed by dosing while inpatient at the CRU. Participants will receive 3 consecutive once-daily doses of either LY3493269 or placebo on Days 1 through 3. Fasting requirements including food and water restrictions must be adhered to for each dose administered (Section 6.1.1). Participants should complete the study assessments and procedures planned during this period as specified in Section 1.3. Unless the investigator identifies a safety concern, participants may be discharged from the CRU on Day 5.

Pharmacokinetic and PD sampling and safety assessments will be performed according to the SoA (Section 1.3). Pharmacokinetic and PD sampling schedules may be modified based on the available safety and PK/PD data.

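### Neither standard noncompartmental formula gives a valid CL/F or V/F for LY3493269 from the planned areas: AUC(0-∞) is taken only after the third daily dose, and steady state is not reached

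*SAP*

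**What the plan says.** Each participant on active drug takes three daily doses: "Participants will receive 3 consecutive once-daily doses of either LY3493269 or placebo on Days 1 through 3" (Protocol 4.1.2).

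SAP 9.3.1 says that the PK parameters of LY3493269 and SNAC "will be calculated using standard noncompartmental methods of analysis". Cmax and AUC(0-24) are computed after each of the three doses. AUC(0-tlast) and AUC(0-∞) are "also calculated after the third dose", with no such area planned for dose 1. The section then adds: "Other parameters, such as half-life, apparent clearance, and apparent volume of distribution, may be reported". Neither document says which dose, which area or which occasion enters CL/F or V/F, and neither mentions a correction for carry-over.

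Two statements in the protocol bear on this. Section 2.2.1 describes the subcutaneous data as showing "a half-life of days, which is suitable for a weekly dosing interval" (the number is redacted), and Section 4.2 expects systemic disposition to be similar whatever the route. Section 4.2 also says that "PK exposures from a short dosing duration of 3 days from this study are not expected to reach steady state for the respective doses".

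Protocol 9.4.4 leaves room for a model-based analysis of LY3493269 and says that "data may be combined with Study GZHA for further analysis". SAP 9.3.2 analyses dose-normalized Day 3 AUC(0-tlast) and AUC(0-∞) and reports least-squares means and between-treatment ratios. It does not say what dose is the divisor.

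**The concern.** Standard noncompartmental practice offers two routes to apparent clearance. One divides a dose by AUC(0-∞) and needs that area to come from that dose alone. The other divides a dose by the area over one dosing interval and needs steady state. The planned AUC(0-∞) starts at the third dose and includes what is left of the first two, so the first condition fails. The protocol itself says that the second fails. Apparent volume, taken from clearance and the terminal slope, inherits whichever error is made.

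The two errors point in opposite directions. Two analysts who both follow SAP 9.3.1 could therefore report clearances several-fold apart, and nothing in the document would show which to believe. A related misreading is possible in SAP 9.3.2: a dose-normalized Day 3 AUC(0-∞) mean, divided by one daily dose, looks like single-dose exposure per mg and is not.

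**Working it through.** The documents give no CL/F, V/F or bias figure, so there is nothing of the plan's own to reproduce.

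**Inputs**
- Three equal daily doses, interval τ = 1 day (Protocol 4.1.2).
- AUC(0-∞) after dose 3 only; AUC(0-24) after each dose (SAP 9.3.1).
- Half-life in days, value redacted (Protocol 2.2.1). *Assumption:* 3 to 7 days, with 1 and 14 days as wider limits.
- *Assumptions:* linear kinetics, mono-exponential decay, equal bioavailability at each dose.

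**Set-up.** Let r = 2^(−1/t½) be the fraction remaining after one day, and set the single-dose AUC(0-∞) to 1, so that the true CL/F equals Dose/1.

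**Formula A: Dose / AUC(0-∞) after dose 3.** The area from dose 3 onward is 1 from dose 3, r from dose 2 and r² from dose 1. CL/F is too low by 1 + r + r². Vz/F = Dose/(λz × AUC(0-∞)) is too low by the same factor. Since r < 1, the factor cannot exceed 3.
- 3 days: 1 + 0.794 + 0.630 = 2.42
- 5 days: 1 + 0.871 + 0.758 = 2.63
- 7 days: 1 + 0.906 + 0.820 = 2.73

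**Formula B: Dose / AUC(0-24) on Day 3.** That area is (1 − r)(1 + r + r²) = 1 − r³. CL/F is too high by 1/(1 − r³).
- 3 days: 1/(1 − 0.500) = 2.00
- 5 days: 1/(1 − 0.660) = 2.94
- 7 days: 1/(1 − 0.743) = 3.89

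| Half-life | A: CL/F and Vz/F too low by | B: CL/F too high by |
|---|---|---|
| 1 day | 1.75 | 1.14 |
| 3 days | 2.42 | 2.00 |
| 5 days | 2.63 | 2.94 |
| 7 days | 2.73 | 3.89 |
| 14 days | 2.86 | 7.25 |

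Formula A is off by more than 2-fold once the half-life passes about 1.44 days. At 5 days the two formulas give clearances 2.63 × 2.94 ≈ 7.7-fold apart. Adding first-order absorption (1 per hour, assumed) changes the factors by less than 0.1 for half-lives up to 8 days.

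**A valid alternative.** The total area from first dose to infinity is 3, so 3 × daily dose / total area returns the true CL/F. The part before dose 3 is 3 − (1 + r + r²), a share of 19.2%, 12.4% and 9.1% of the total at 3, 5 and 7 days. Leaving it out, by dividing the post-dose-3 area alone by 3 × dose, would understate exposure per mg by the same 9 to 19%.

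**Sampling in that window.** The Schedule of Activities shows PK samples to 12 h on Day 1, none on Day 2, then Day 3 predose, so about 36 of the first 48 h must be interpolated. At a 5-day half-life a straight line across the gap gives 0.5 × (0.129 + 0.226) × 1.5 = 0.266, against a true 0.305. The shortfall of 0.038 is 0.038/3 = 1.3% of the total area. At 7 and 3 days it is about 1% and 2%.

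**The case against.** The strongest reply is that no wrong formula is written down. CL/F and V/F are optional, they are neither primary nor secondary endpoints, the sponsor's pharmacokineticists may well correct for carry-over, and Protocol 9.4.4 already permits a model. The SAP also marks the areas as following the third dose. All of this stands, and it is why the conclusion is conditional on the parameters being reported. It does not remove the problem: the only method named is standard noncompartmental analysis, and neither of its usual formulas fits the planned areas.

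Several stronger readings are tempting, and the documents do not support them:
- *That clearance will be wrong 2- to 4-fold because of carry-over.* Carry-over in AUC(0-∞) is capped at 3-fold. Figures near 4 belong to the Day 3 AUC(0-24) formula, whose error has the opposite sign.
- *That oral bioavailability or dose selection will be distorted.* No objective or endpoint compares oral with subcutaneous exposure, and combining data with Study GZHA is only a possibility. Safety data are the primary criteria for escalation (Protocol 6.6.1). The stated bioavailability question, 300 against 600 mg SNAC at 24 mg (Protocol 4.3), is a between-cohort ratio.
- *That the dose-proportionality results are biased.* Under linear kinetics with a common half-life, the carry-over factor is the same in every cohort and cancels in the ratios and their confidence intervals.
- *That half-life or SNAC is affected too.* The terminal slope is unchanged under linear kinetics. No SNAC half-life is given, and the error vanishes when half-life is short against 24 h (factor 1.00 at 0.1 day).

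**Conclusion.** The point holds for CL/F and V/F of LY3493269, if they are reported. With a half-life of 3 to 7 days, the single-dose formula on AUC(0-∞) after dose 3 would understate CL/F and Vz/F by about 2.4 to 2.7 times, with a ceiling of 3. The steady-state formula on the Day 3 AUC(0-24) would overstate CL/F by about 2.0 to 3.9 times.

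The sizes rest on an assumed half-life, because the value is redacted, and on linear kinetics with equal average bioavailability at each dose. They are systematic factors: Protocol 4.2 expects very high variability in absorption within a participant, so individual values will scatter around them. That neither formula is valid does not depend on the exact half-life. It follows from a half-life of days and the protocol's own statement on steady state.

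The consequence is limited to optional secondary-level PK output and to anyone who later reads those values, or the dose-normalized Day 3 means, as single-dose quantities.

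**What to change.** In SAP 9.3.1:
- Label AUC(0-∞) and AUC(0-tlast) after dose 3 as including carry-over from doses 1 and 2.
- For LY3493269, derive CL/F as 3 × daily dose / total area from first dose to infinity, and V/F from that CL/F and the terminal slope. Alternatively, take both from the model-based analysis that Protocol 9.4.4 allows, or state that they will not be reported.

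In SAP 9.3.2, state that the dose-normalized Day 3 areas serve between-cohort ratios only and are not single-dose exposure per mg. Dividing the post-dose-3 area by three doses is not a substitute, because it leaves out the area before dose 3.

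The cost is a few lines of SAP text and one derivation, with no new samples. The drawback is that, without Day 2 samples, most of the first 48 h is interpolated and the dose-2 peak is not observed. That window holds about 9 to 19% of the total area at half-lives of 7 to 3 days, so the possible error is small beside the 2- to 4-fold errors of the two default formulas.
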